## **3.4 Safety analysis**

### **3.4.1 General consideration for safety analysis**

#### Analysis population

All safety endpoints will be evaluated in the safety population as defined in Section 3.1.

#### Methods of Analysis

All adverse events (AEs) and serious adverse events (SAEs), vital sign measurements, physical examination findings, will be evaluated for safety. Safety data will be summarized using descriptive statistics by treatment group and overall.

### **3.4.2 Clinical Adverse Events**

For this study, any AE experienced by the subject after ICF sign-off through the end-of-study visit is to be recorded on the CRF, regardless of the severity of the event or its relationship to the investigational drug (administered in Study 215ON201) or procedure(s) in this study. Any SAE experienced by the subject between the time the subject has signed the ICF and the End of Study Visit is to be recorded on an SAE Form, regardless of the severity of the event or its relationship to the investigational drug (administered in Study 215ON201) or procedure(s).

All AEs will be coded using the MedDRA. The overall summary table of AEs will present the number of subjects with the following events for each treatment group and overall. A subject is counted only once in each category.

- AE;
- AE with severity as “moderate” or “severe”;
- AE with severity as “severe”;
- investigational drug (administered in Study 215ON201) related AE
- study procedure(s) related AE;
- SAE;
- AE leading to withdrawal from study.

The incidence of AEs will be summarized using the primary system organ class and preferred term. Preferred terms are presented by decreasing incidence in the total column within each system organ class. The incidence of AEs will also be summarized by event severity and by relationship to the investigational drug (administered in Study 215ON201) or study procedure(s) using system organ class and preferred term. Within each system organ class or/and preferred term, the same subject will be counted only once. If a subject

has more than one AE in the same system organ class or/and preferred term, the most severe AE will be reported.

Additionally, the incidence of AEs will be summarized by using preferred term only, and preferred terms will be ordered by decreasing frequency of AEs in the BIIB033 100mg/kg column.

The incidence of SAEs will also be summarized by primary system organ class and preferred term and treatment group as well.

Listings of all AEs, SAEs, and AEs that led to study withdrawal will be presented.

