14.2.2.1. Adverse Events

AEs will be coded using the Medical Dictionary for Regulatory Activities. The incidence of clinical AEs will be summarized by severity and by relationship to study procedure(s) and to prior treatment with investigational drug (administered in Study 215ON201). The summary tables will include incidence estimates for overall system organ class as well as for preferred terms within each system organ class.

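### The SAP's most-severe-AE rule is not limited to the severity tables, so in the by-relationship tables it can count a subject with a related AE as not related

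*SAP*

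**What the plan says.** Protocol version 4.0, Section 14.2.2.1, promises two breakdowns of adverse events: "The incidence of clinical AEs will be summarized by severity and by relationship to study procedure(s) and to prior treatment with investigational drug". It gives no rule for a subject with several events.

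SAP Section 3.4.2 carries this out at two levels.

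- **Overall summary table.** It has separate lines for "investigational drug (administered in Study 215ON201) related AE" and "study procedure(s) related AE", with the rule "A subject is counted only once in each category". A subject with any related AE therefore appears on the matching related line, whatever else that subject reported.
- **Tables by system organ class and preferred term.** One sentence introduces both breakdowns: "The incidence of AEs will also be summarized by event severity and by relationship to the investigational drug", and also to study procedures. The next sentence sets the counting unit: "Within each system organ class or/and preferred term, the same subject will be counted only once". The one after it says which event is kept: a subject who "has more than one AE in the same system organ class or/and preferred term, the most severe AE will be reported".

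Neither of the last two sentences is confined to the severity table. The same section also promises listings of every AE.

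**The concern.** Keeping the most severe event is the natural choice for a severity table. A relationship table asks a different question: did this subject have any event in this class that the investigator attributed to the drug or to a procedure? Choosing the event by severity can answer that wrongly when the attributed event is the milder of two.

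At stake is one of the two AE breakdowns that the protocol promises. No drug is given in this follow-up study, so attribution to study procedures, or to prior BIIB033, is the main thing a reader would look for in the class-level tables. Two tables from the same SAP section could also give different answers for the same subject.

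**Working it through.** The plan states no figure on this point, so there is none to reproduce. The check applies the written rule to individual cases and then asks how many subjects could be affected.

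**1. Is there a relationship rule elsewhere?** The rest of the SAP safety section (3.4.1 and 3.4.2) has none, and neither does Protocol 14.2. Protocol 13.2.2 defines relationship as two categories, related and not related. SAP Appendix 1 is headed as example code for Sections 3.3.1 and 3.3.3 only, so it does not claim to cover safety tables.

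**2. Worked cases: one subject, all events in the same class or term.**

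| Events | SAP rule as written | Related if any AE is related | Overall related-AE line |
|---|---|---|---|
| Mild related + severe not related | Not related | Related | Counted |
| Mild related + mild not related | Undetermined (tie) | Related | Counted |
| Severe related + mild not related | Related | Related | Counted |
| Mild related only | Related | Related | Counted |

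Only the first two rows can go wrong, and only from related to not related. A subject with no related AE cannot be moved the other way.

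**3. Conditional share (assumption only).** Take subjects who have one related and one not-related AE in the same class, with independent severities and mild/moderate/severe proportions p1, p2, p3.

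- Related AE strictly milder: p1(p2 + p3) + p2·p3
- Tie: p1² + p2² + p3²

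| Assumed mix | Strictly milder | Tie |
|---|---|---|
| 80/15/5% | 0.80×0.20 + 0.15×0.05 = 17% | 67% |
| 60/30/10% | 0.60×0.40 + 0.30×0.10 = 27% | 46% |
| 40/40/20% | 0.40×0.60 + 0.40×0.20 = 32% | 36% |

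If ties are split evenly, the share is 50% for any mix, by symmetry.

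**4. How many such subjects?** The documents give no AE frequencies for this study. A rough guide comes from Study 215ON201: 83% of subjects had an AE (Protocol 5.5.2), with visits to Week 32, or 224 days (Protocol 5.6). Assume a constant rate and a 6-day recording period (1 day + 5).

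- Chance of any AE: 1 − exp(−[−ln(1 − 0.83)] × 6/224) = 1 − exp(−1.772 × 0.0268) ≈ 4.6%
- Of 82 subjects: 82 × 0.046 ≈ 3.8

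Assume generously that all 3.8 have a related AE.

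- Low case, where a second, not-related AE in the same class is as likely as any AE (4.6%) and only strictly milder events are lost (60/30/10% mix): 3.8 × 0.046 × 0.27 ≈ 0.05 subjects.
- High case, with an assumed 50% co-occurrence and ties split: 3.8 × 0.50 × 0.50 ≈ 0.95 subjects.

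The range is roughly zero to one subject. The parent-study rate is only a guide. Many procedures on one day could raise the AE rate, events may cluster within subjects, and fewer than 82 may enrol.

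**The case against.** The strongest reply is that this is loose wording with little consequence. Its parts differ in force.

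- **Table layout.** The SAP does not fix the layout of the relationship tables. A programmer who first selects related AEs and then counts each subject once would avoid the problem. That is true, but the SAP does not say to do it, and the literal sequence of sentences points the other way.
- **The information survives.** The overall summary still counts every subject with a drug-related or procedure-related AE, and all AEs are listed. With at most 82 subjects the listings can be read in full. This stands.
- **No inference depends on it.** Safety is summarised descriptively (SAP 3.4.1). Protocol 9.3 keeps original treatment from the sites, and investigators judge relationship, so no distortion between the original treatment groups is apparent. This stands.
- **Drug-related events should be rare.** Dosing ended at least two years earlier, and the reported half-life is about 2 to 3 weeks. In practice the point mainly concerns procedure-related events.

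A reader might infer that every milder related AE will be reported as not related. The documents do not support that. The subject must also have a more severe (or tied) not-related AE in the same class or term; no event is recoded, and a lone related AE is counted correctly. A reader might also be tempted to attach a percentage understatement to related incidence. That would need the frequency of a related and a not-related AE in the same class within a few days, which the documents do not give.

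**Conclusion.** The point holds, as a minor one. The SAP states a selection rule that, read literally, uses the wrong attribute for the relationship tables and leaves ties unresolved. Relative to an any-related count, its only possible effect is to lower related incidence in class-level or term-level rows, which can then conflict with the related-AE lines of the overall summary. Those overall counts, the listings and the severity tables are unaffected.

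The number of subjects affected is probably zero or one. That rests on the 82-subject ceiling, the one-visit (+5-day) recording period and the assumed rates shown above. It is a judgement of scale, not an estimate to quote.

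**What to change.** In SAP 3.4.2, confine the most-severe sentence to severity tables and add a relationship rule, for example:

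*In tables by severity, a subject with several AEs in the same system organ class or preferred term is counted once, at the highest severity. In tables by relationship, such a subject is counted once, as related if any of those AEs is related. The relationship rule is applied separately for the 215ON201 investigational drug and for study procedure(s).*

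This supplies the missing tie rule and brings the class-level and term-level tables into line with the overall summary. It costs one SAP amendment of a sentence or so and one programming sort key, with no new data. The downside is that related counts may be slightly higher.

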### 3.4.3 Vital Sign Measurements

The analysis of vital signs will focus on the incidence of potentially clinically relevant abnormalities. The criteria for potentially clinically relevant abnormalities are given in Table 2.

**Table 2: Criteria to Determine Potentially Clinically Relevant Abnormalities in Vital Signs**

Vital Sign	Criteria for Abnormalities
Temperature	>38°C
Pulse	>100 beats per minute (bpm) <40 bpm
Systolic Blood Pressure	>160 mmHg <90 mmHg
Diastolic Blood Pressure	>100 mmHg <45 mmHg

A summary table for subjects with any potentially clinically relevant abnormalities will be provided. In the summary table, entries are numbers of subjects with an abnormality divided by number of subjects evaluated followed by corresponding percentages. Number evaluated is the number of subjects who had a baseline assessment and at least one post-baseline assessment for that vital sign.

The count and percentage of subjects with weight change of greater than 7% from baseline at Day 1 will be summarized by treatment group. A subject listing of weight change of greater than 7% from baseline at Day 1 will be presented.

For temperature, pulse, systolic blood pressure, diastolic blood pressure, and weight, actual values and changes from baseline will also be summarized using descriptive statistics by treatment group at day 1.

A subject listing will also be presented for subjects with any abnormalities in vital signs. In this listing, each subject's complete vital sign values including the baseline values will be listed with abnormalities labeled.

### 3.4.4 Physical Examination

The result collected on CRF at Day 1 will be listed as performed or not performed, and abnormality will be reported as AE.

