4.2. Schedule of Activities

Table 1: Schedule of Activities

Tests and Assessments ¹	Day 1 ² : (2 Years + up to 12 Months After Week 32 Visit in Study 215ON201 or Projected Week 32 Visit if the Subject Did Not Complete All Visits)
Informed Consent	X
Eligibility Criteria Check	X
Medical History ³	X
Multiple Sclerosis Diagnosis	X
Multiple Sclerosis Signs and Symptoms	X
Concomitant Therapy and Procedures Recording	X
Vital Signs ⁴	X
Physical Examination	X
Expanded Disability Status Scale ⁵	X
Symbol-Digit Modalities Test	X
Multiple Sclerosis Functional Composite Including 
 • Timed 25-Foot Walk • 9-Hole Peg Test (Dominant and Nondominant Hands) • (3-Second) Paced Auditory Serial Addition Test 	X

CONFIDENTIAL

The information contained herein may not be used, disclosed, or published without the written consent of Biogen MA Inc.

Tests and Assessments ¹	Day 1 ² : (2 Years + up to 12 Months After Week 32 Visit in Study 215ON201 or Projected Week 32 Visit if the Subject Did Not Complete All Visits)
[REDACTED]	[REDACTED]
Full-Field Visual Evoked Potential ⁷	X
[REDACTED]	[REDACTED]
Adverse Event/Serious Adverse Event Recording ¹²	X

[REDACTED] MRI = magnetic resonance imaging.

¹ All assessments should be performed on the same day and in the order listed, when possible (or within a +5-day window of the 1-day visit).

² Completion of the Day 1 visit assessments constitutes the end-of-study visit.

³ Medical history will be taken from after last study visit in Study 215ON201.

⁴ Vital signs include temperature, systolic and diastolic blood pressure, pulse rate, body weight, and respiratory rate (after sitting for at least 5 minutes).

⁵ Expanded Disability Status Scale should be performed by a study certified rater. Where applicable, refer to study manual for instructions.

⁶ [REDACTED]

⁷ Sites and technicians must be qualified and approved by the central reader to perform [REDACTED], full-field visual evoked potential, and [REDACTED].

[REDACTED]

¹² Adverse event/serious adverse event monitoring will be recorded after informed consent form sign-off through the end-of-study visit.

CONFIDENTIAL

The information contained herein may not be used, disclosed, or published without the written consent of Biogen MA Inc.

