5.2. Current Therapies for Acute Optic Neuritis

The only currently available treatment for AON is high-dose intravenous (IV) steroids (e.g., methylprednisolone) followed by an oral prednisone taper, which speeds up the recovery of symptoms (e.g., ocular pain) and high-contrast visual acuity (HCVA) primarily in the first 2 weeks after an attack, but has no long-term beneficial effects on the ultimate recovery of visual function [Beck 1992] nor is there evidence that it affects the degree of axonal loss or conduction velocity in the optic nerve pathway.

Despite treatment with high-dose steroids, over 60% of patients with AON are left with loss of visual function [Kupersmith 2007].

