7.2.3. Visit Schedule

Each subject will have approximately 1 scheduled study visit (with a +5-day window of the 1-day visit) that is dependent on the scanner capabilities and equipment availability at each clinical site.

CONFIDENTIAL

The information contained herein may not be used, disclosed, or published without the written consent of Biogen MA Inc.

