13.1. Definition

13.1.1. Adverse Event

An AE is any untoward medical occurrence in a patient or clinical investigation subject administered a pharmaceutical product and that does not necessarily have a causal relationship with this treatment. An AE can therefore be any unfavorable and unintended sign (including an abnormal laboratory finding), symptom, or disease temporally associated with the use of a medicinal (investigational) product, whether or not related to the medicinal (investigational) product.

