13.3. Monitoring and Recording Events

13.3.1. Adverse Events

Any AE experienced by the subject after ICF sign-off through the end-of-study visit is to be recorded on the CRF, regardless of the severity of the event or its relationship to study procedure(s) and/or to prior treatment with the investigational drug (administered in Study 215ON201).

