14.2.2. Methods of Analysis

All AEs, clinical laboratory abnormalities, vital sign measurements, and physical examination findings will be evaluated for safety.

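### SAP 3.4.4 reports any Day 1 physical-examination abnormality as an AE, which conflicts with the post-consent AE window in SAP 3.4.2 and Protocol 13.3.1

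*SAP*

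**What the plan says.** SAP 3.4.4 is a single sentence: "The result collected on CRF at Day 1 will be listed as performed or not performed, and abnormality will be reported as AE". It does not refer to onset, to the 215ON201 examination, or to worsening.

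The collection rule is narrower. SAP 3.4.2 states that "any AE experienced by the subject after ICF sign-off through the end-of-study visit is to be recorded on the CRF", and Protocol 13.3.1 (version 4.0) has the same window: "Any AE experienced by the subject after ICF sign-off through the end-of-study visit is to be recorded on the CRF". The AE definition in Protocol 13.1.1 does not settle the matter, because it is broad and does not exclude conditions already present and unchanged: "An AE can therefore be any unfavorable and unintended sign (including an abnormal laboratory finding), symptom, or disease temporally associated with" use of the product.

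The window is very short. Protocol Table 1 schedules consent and the physical examination on Day 1, to be done the same day and in the listed order where possible, otherwise within +5 days. A footnote to that table adds: "Completion of the Day 1 visit assessments constitutes the end-of-study visit".

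On reporting, Protocol 14.2.2 says: "All AEs, clinical laboratory abnormalities, vital sign measurements, and physical examination findings will be evaluated for safety". SAP 3.4.1 likewise names physical examination findings among the items to be evaluated, and says safety data will be summarized by treatment group and overall.

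**The concern.** Two sections of the SAP give different answers for the same finding. Suppose the Day 1 examination shows a sign that has been stable for a year. Under 3.4.4 it is an AE. Under 3.4.2 and Protocol 13.3.1 it is not, because it was not experienced after consent. Nothing says which section prevails.

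This matters because of the design. In a trial with months of follow-up, a few misfiled standing findings would be diluted by genuine events. Here the AE window lasts from one to six days, so standing findings could make up much of the AE table. SAP 3.4.2 tabulates AEs by original treatment group, by severity, and by relationship to the parent-study drug or to study procedures. A standing finding entered as an AE would need a severity grade and a relatedness judgement, and would then be read as on-study safety information. With approximately 33 sites planned, some may follow one rule and some the other.

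A second gap sits in the same sentence. If a site follows the narrower window and does not record an old finding as an AE, the examination output in 3.4.4 shows only that the examination was performed. No listing or table of examination findings as such is planned, despite SAP 3.4.1.

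**Working it through.** The plan states no figure on this point, so there is nothing to reproduce. The check is a side-by-side reading, followed by an illustration of scale.

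**Reading**

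1. Trigger for an AE. SAP 3.4.4: any abnormality. SAP 3.4.2 and Protocol 13.3.1: experienced after consent and up to the end-of-study visit. The first set is wider than the second.
2. Length of the window. Consent and examination are both Day 1 items, and the +5-day allowance makes the longest window 1 + 5 = 6 days.
3. Is there a filter elsewhere? Protocol 13.4.1 has the investigator determine onset dates, but the SAP states no rule that uses them. There is no treatment-emergent definition and no rule for pre-existing conditions.
4. Is there another place for standing findings? Medical history starts after the last 215ON201 visit (Table 1, footnote 3; SAP 3.2.4). A residual sign of the original optic neuritis dates from before that, so it falls outside that scope.
5. Comparison with the neighbouring section. SAP 3.4.3 gives vital signs explicit criteria, changes from baseline, summaries by group and a listing of abnormal subjects. SAP 3.4.4 has none of these.

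**Scale (illustration only)**

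Input from the documents: 82 subjects dosed in 215ON201, 41 per arm (Protocol 5.5.2). This is the maximum enrolment. Assumption: the prevalence *p* of a standing abnormality noted at the examination, which the documents do not give.

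Expected subjects per arm with an AE from the examination alone = 41 × *p*:

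| Assumed *p* | Per arm |
|---|---|
| 5% | 41 × 0.05 = 2.1 |
| 10% | 41 × 0.10 = 4.1 |
| 20% | 41 × 0.20 = 8.2 |

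Counts fall in proportion if fewer subjects enrol.

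For comparison, here is a rough figure for genuinely new AEs. In 215ON201, 34 of 41 subjects per arm had an AE (Protocol 5.5.2). Assume a constant hazard over 32 weeks (224 days):

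- *h* = −ln(1 − 34/41) / 224 = 0.0079 per day
- 1 day: 41 × (1 − e^(−*h*)) = 0.3 subjects per arm
- 6 days: 41 × (1 − e^(−6*h*)) = 1.9 subjects per arm

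The parent study included infusions, so this hazard is only a rough guide. On these assumptions, a 10% prevalence of standing findings would outnumber new events.

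Chance imbalance: with two independent binomials of 41 and no true difference, the probability that the arms differ by 5 or more such subjects is 0.096 at *p* = 10% and 0.213 at *p* = 20%.

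**The case against.** The strongest reply is that sites record AEs under the protocol, not the SAP. Protocol 13.3.1 limits recording to events after consent, and 13.4.1 requires onset dates. SAP 3.4.4 can then be read as a note on presentation: abnormalities that qualify as AEs reach the tables through the AE module. That reading is reasonable and may be what was meant. It is not what the sentence says, however, so the sentence still needs correcting.

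It is also fair that the consequence is limited. No drug is given, safety summaries are descriptive, and sites remain blinded to the parent-study arm, so uneven site practice is not shown to produce a systematic difference between arms.

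Three stronger readings may tempt a reader, and the documents do not support them.

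- *About 25 subjects per arm would carry a spurious AE.* This applies the statement in Protocol 5.2 that "over 60% of patients with AON are left with loss of visual function" to 41 subjects (0.60 × 41 = 24.6). That is a literature rate of visual loss, not a rate of abnormality on a general physical examination. Protocol 5.6 says the 215ON201 subjects recovered clinically to a large extent.
- *The findings are never tabulated.* Any finding reported as an AE is counted by system organ class and preferred term, by arm. Neurological deficits also appear by arm under MS signs and symptoms and under the EDSS functional systems (SAP 3.3.3). What is missing is a display of examination findings as such.
- *A real drug benefit would show up as fewer AEs on BIIB033.* This requires the arms to differ in deficits visible on examination. Protocol 5.6 describes clinical recovery regardless of treatment assignment.

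**Conclusion.** The point stands as a conflict between stated rules: SAP 3.4.4 is wider than the AE window it should serve, and it has no condition for new or worsened findings. With one examination at or within days of consent, most abnormalities can be expected to pre-date consent. The literal rule would therefore mix standing findings into the AE tables by arm. It does not follow that every old deficit will become an AE, because the protocol's window and the onset dates allow a site to exclude it. The defect is that the documents support both practices.

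The size cannot be derived from the documents. About 4 subjects per arm rests on an assumed 10% prevalence and full enrolment of 41 per arm, and serves only to show that a modest prevalence is large next to a window of one to six days.

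The second part also stands: a performed/not-performed listing does not deliver what SAP 3.4.1 says about examination findings. Both parts affect descriptive safety output only. The primary FF-VEP analysis is unaffected.

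**What to change.** Replace the second half of SAP 3.4.4 with:

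> An abnormality is reported as an AE only if it is new or worsened after ICF sign-off; abnormalities present before ICF sign-off are not counted in the AE tables and are given in a by-subject listing with treatment group.

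Add a matching CRF completion note so that all sites apply the same rule. The onset date that Protocol 13.4.1 already requires is enough to apply it to reported events. SAP 3.4.1 should then state that examination findings are presented through the AE tables and this listing, since a listing is not a summary.

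Leave the scope of medical history unchanged. Sending residual optic neuritis findings there would contradict Table 1, footnote 3, and SAP 3.2.4, both of which start at the last 215ON201 visit.

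The cost is one SAP sentence, a conforming phrase in 3.4.1, the CRF note and one extra listing. The CRF is not among the documents. If it holds only performed/not performed, it also needs a field describing the abnormality. Reported AE counts will be lower than under the literal rule.
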